**Red Cell Storage Duration and Outcomes in Cardiac Surgery:
A Randomized Controlled Trial**

[name] [name], MS, FACC and Colleagues
Departments of Cardiothoracic Anesthesia and Outcomes Research

NCT 00458783

Cleveland Clinic
[name]
[name]

[contact]
[contact]
E-mail: [contact]

Currently RBC units that have been stored up to 42 days are available for transfusion. Increasing RBC storage duration has been shown to alter red cells by reducing oxygen availability, creating proinflammatory and immunomodulatory effects, as well as reducing red cell deformability, and aggregability. Prior observational investigations report variable results in terms of morbid outcomes related to increasing length of RBC storage. We propose a randomized blinded clinical trial with a maximum enrollment of 2840 adult cardiac surgical patients. Consecutive consenting patients who meet the inclusion criteria will be randomized to 'age of blood' less than two weeks or greater than 20 days shelf life for all of the units allocated to the patient. The trial uses a group sequential design with three internal interim analyses that examine group sequential boundaries of both efficacy and futility. The overall type I error rate is 0.05 and power is 85%. The study we propose will provide an appropriate level of evidence for determining whether increased storage duration is associated with increased morbidity. We estimate that it will take approximately 2-3 years to complete the enrollment and randomization.

Personnel

Name	Organization	Role on Project
[name] [name], MS	CCLMC-CWRU*	Principal Investigator
[name]	CCLMC-CWRU	Co-investigator,
[name]	CCLMC-CWRU	Co-investigator,
[name]	CCLMC-CWRU	Principal statistician
[name]	CCLMC-CWRU	Co-investigator, Cardiothoracic anesthesiologist
[name]	CCLMC-CWRU	Co-investigator, Cardiothoracic anesthesiologist
[name]	CCLMC-CWRU	Co-investigator, cardiothoracic surgeon
[name]	CCLMC-CWRU	Co-investigator, cardiothoracic surgeon
[name]	CCLMC-CWRU	Co-investigator, cardiothoracic surgeon
[name]	CCLMC-CWRU	Co-investigator, cardiothoracic surgeon
[name]	CCLMC-CWRU	Co-investigator, Laboratory medicine/ Clinical pathology
[name]	CCLMC-CWRU	Co-investigator, Laboratory medicine/ Clinical pathology

*Cleveland Clinic Lerner College of Medicine, Case Western Reserve University

Executive Committee

Name	Role
[name], MS	Chair
[name]	Member
[name]	Member
[name]	Statistician, non-voting

A. Specific Aims

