This trial is a single center, two-arm parallel design with two interventions: newer blood versus older blood. Patients randomized to the newer blood group will receive blood units that have been stored less than or equal to 14 days; patients randomized to the older blood group will receive blood units that have been stored more than or equal to 20 days. The primary outcome is a binary composite outcome composed of major and minor postoperative morbid events defined by STS definitions. The secondary outcomes include prolonged postoperative ventilation and occurrence of atrial fibrillation, length of intensive care unit and length of hospital stay. These outcomes will be assessed by research assistants blinded to the treatment assignment. All the outcomes are short-term endpoints that can be ascertained within a few weeks after the operation, which makes it possible to do sequential monitoring. The randomized groups will be descriptively compared on all baseline variables using summary statistics such as mean and standard deviation, median and quartiles or frequency and percent, as appropriate. No two-sample tests on baseline variables are necessary, but those that are believed to be strongly correlated with the outcomes will be included in the covariate adjustment in the primary and secondary analyses. The level of statistical significance used in the primary analysis will be 0.05, and all tests in the primary and secondary analyses are two-tailed. The statistical analysis will be performed using SAS 9.1 (SAS Institute, Cary, NC).

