If a patient meets the inclusion criteria and gives consent, he/she could potentially be randomized in the trial. Before the start of surgery, the research coordinator responsible for randomization will check the randomization list and determine that person's randomization allocation. The coordinator will then contact the blood bank and check whether there are adequate type-matched newer or older blood units available for that patient. Occasionally, there is short of supply of newer or older blood for a certain blood type. If the Blood Bank can not ensure that the patient receive only the kind of blood he/she is randomized to receive, that patient will be taken out of the trial and not randomized. We expect that this failure of randomization occurs infrequently, and it more likely occurs to patients with rare blood types. Since there is no evidence for an interaction between rare blood types and age of blood, this practice is not expected to introduce bias to the study. Another situation that may cause failure of randomization is that the patient may not need any transfusion for the entire hospital stay as determined by the surgeon. In that case the patient will also be taken out of the trial at hospital discharge. We expect that about 40-50% patients will not need any transfusion. This is a special kind of drop-out after randomization. However, since the dropping out is not related to the treatment assignment, we do not believe it will introduce bias to the study, and the two treatment arms will still be balanced.

The primary analysis is a two-sided chi-square test comparing the two treatment groups on the rate of composite outcome, based on the intent-to-treat (ITT) principal. The 95% confidence interval of the rate of

composite outcome will be calculated for the two treatment groups, and for the treatment effect which is quantified by the odds ratio.

We will test the interaction between the treatment groups and the recipients' blood type, and donors' blood type. In this way, we may identify subgroups more sensitive to the treatment. Although pre-specified, we will interpret the estimated interactions and their statistical significance with much caution due to multiplicity and they are not the primary analysis or focus. Our assessment of interactions will be viewed as exploratory and hypothesis generating.

Sample Size Calculation and Sequential Monitoring

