The sample size calculation is based on the primary analysis, which is a Chi-squared test comparing the proportion of composite outcome between the two randomized groups. We estimate that the unadjusted odds ratio of the composite outcome between older and newer blood groups is 1.21 (25.9% vs. 22.4%). The adjusted odds ratio is 1.16 (95% confidence interval 1.01-1.33). That result was from a comparison between age of blood less than 14 days versus more than 14 days. For this trial we expect a bigger effect because we define the older group as age of blood being longer than 20 days instead of 14 days. Therefore, for this sample size calculation we assume the odds ratio is 1.3. The overall proportion of composite outcome is estimated to be roughly around 30% in an observational data set from CVIR. These two assumptions lead to the estimated composite event rate of the newer blood group being 27.3% and that of the older blood group being 32.7%. If we set the type I error to be 0.05 and power to be 0.85, the study would need to enroll 1328 transfused patients per treatment arm, for a total of 2656 patients with equal assignment. The total sample size could increase to 4810 transfused patients if the odds ratio is 1.2 (32% vs. 28%), and it becomes 1600 if the odds ratio is 1.4 (33.5% vs. 26.5%).

We plan on three interim analyses at 25%, 50%, 75% of the accrual, plus the final analysis. Our calculations of group sequential boundaries assume non-binding stopping rules and account for monitoring both the null (efficacy) and alternative hypothesis (futility). We use the gamma family spending function with gamma = -4 for efficacy and gamma = -2 for futility, which is between Pocock and O'Brien-Fleming approaches **Figure 9**. We are thus spending beta somewhat faster than the alpha during the trial, allowing for early termination if there is little treatment group difference. The stopping boundaries are shown in **Figure 10** (on the scale of Z-statistic of two-sample proportions test) and Table 1 (on the *P* value scale). The total sample size has to be modified up a bit (n=2838) in order to properly account for the interim looks. Note that this is the maximum sample size for this study. Because the group sequential design makes it possible to terminate the study early for either efficacy or futility, the expected sample size is 2004 if the null hypothesis of no difference is true and it is 2063 if the alternative hypothesis (27.3% vs. 32.7%) is true.

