Table 1. Stopping boundaries on the *P* value scale and probabilities of crossing the boundaries (H0: there is no difference in the proportions of composite outcome between the treatment groups; H1: there is a difference)

P value threshold	Interim 1 (n=708)	Interim 2 (n=1418)	Interim 3 (n=2128)	Final (n=2838)
To reject H0, p must be less than or equal to	0.0016	0.0048	0.0147	0.044
To reject H1, p must be larger than or equal to	0.9478	0.7128	0.2424	
Boundary crossing probability under H0	0.054	0.271	0.472	0.203*
Boundary crossing probability under H1	0.071	0.251	0.376	0.302*

* Probability of reaching the final analysis without early boundary crossing

We assume stable enrollment (uniform accrual) during the trial. Based on the number of cardiac surgeries conducted at the Cleveland Clinic each year, we estimate that it may take 2-3 years to complete the enrollment. The clinical endpoint can usually be determined within 30 days after the operation. Therefore, the interim/final

analyses will be performed at six months, one year, one and half year, and two year. The probabilities of crossing (at least one) boundary at each interim looks are calculated in Table 1. The stopping rules presented here will be used for reference by the Data Safety Monitoring Board to make decisions.

In summary, we recommend that the study enroll a maximum of 2840 patients, with 1420 patients in each treatment arm in order to achieve 0.05 type I error and 0.85 power. The enrollment could take 2-3 years. The sample size and grouping sequential boundary calculations were performed using NCSS-PASS (www.NCSS.com) and East 5.0 (Cytel Inc.).

[figure not shown]
[figure not shown]

Figure 10. Grouping sequential boundaries for efficacy (extremes) and futility (middle). If the test statistic (normalized difference of two proportions) crosses the boundaries and enters into the purple or pink areas, we may terminate the trial with claim of either efficacy or futility.

Boundaries efficacy (extremes), futility (middle)

Strengths, Limitations and Significance

Strengths

Cleveland Clinic Heart Center is among one of the largest cardiac surgical programs in the United States. Our procedural volume coupled with the research infrastructure at the Cleveland Clinic will allow for us to perform this study with sufficient power within a time frame of approximately 2-3 years. Our protocol will provide evidence-based medical guidelines for red cell storage duration.

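### The planned 95% interval for the odds ratio is not tied to the four-look design; computed the ordinary way it covers about 92.4% to 93.9% at the plan's alternative and can exclude 1 when the test does not reject.

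*Combined protocol and SAP*

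**What the plan says.** The Statistical Analysis Plan makes a two-sided chi-square test on the composite outcome the primary analysis. The next sentence says that a 95% confidence interval for the rate of "composite outcome will be calculated for the two treatment groups, and for the treatment effect which is quantified by the odds ratio". It gives no method for that interval and does not mention the interim looks.

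The section Sample Size Calculation and Sequential Monitoring sets three interim analyses and a final one. It states: "We use the gamma family spending function with gamma = -4 for efficacy and gamma = -2 for futility". It also states: "Our calculations of group sequential boundaries assume non-binding stopping rules". In the stopping-boundary table (Table 1 of that section), the row for rejecting H0 says that p "must be less than or equal to" 0.0016, 0.0048, 0.0147 and 0.044 at the four looks. The abstract gives the design's target: "The overall type I error rate is 0.05 and power is 85" percent.

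All of this concerns the test. No section describes a repeated, stagewise-ordered or otherwise adjusted interval, or says at what level the interval is computed after an early stop.

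**The concern.** A nominal 95% interval computed as if there had been one analysis does not keep 95% coverage when the data decide at which of four looks the trial stops. It also uses a critical value of 1.96 at the final look, where the test uses 2.014, so interval and test can point different ways. The odds ratio and its interval are what a guideline group would carry forward from this trial. They should therefore have the level they state and agree with the test they accompany.

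**Working it through.** **Inputs.** From Sample Size Calculation and Sequential Monitoring: rates of 27.3% versus 32.7% (alternative), 28% versus 32%, 26.5% versus 33.5%, and 30% overall (used for the null). From its Table 1: looks at 708, 1418, 2128 and 2838 patients, that is 354, 709, 1064 and 1419 per arm; efficacy p of 0.0016, 0.0048, 0.0147 and 0.044; futility p of 0.9478, 0.7128 and 0.2424. As two-sided z values these are 3.156, 2.820, 2.440 and 2.014 for efficacy, and 0.065, 0.368 and 1.169 for futility.

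**Step 1: reproduce the plan's design.** The cumulative alpha spent at fraction t is 0.05 × (1 − e^(4t)) / (1 − e^4), which gives 0.0016, 0.0060, 0.0178 and 0.05 at t = 0.25, 0.5, 0.75 and 1. Solving for the boundaries by numerical integration returns p = 0.0016, 0.0048, 0.0147 and 0.044, exactly as in Table 1. The other figures also agree:

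| Quantity | Plan | Recomputed |
|---|---|---|
| Type I error, futility ignored | 0.05 | 0.0500 |
| Power, futility followed | 0.85 | 0.849–0.851 |
| Stopping at looks 1–3, H0 | 0.054, 0.271, 0.472 | 0.0555, 0.269, 0.472 |
| Stopping at looks 1–3, H1 | 0.071, 0.251, 0.376 | 0.072, 0.250, 0.377 |
| Expected N, H0 and H1 | 2004 and 2063 | 2003 and 2062 |

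So the design being tested is the plan's own, and its test is sound.

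**Step 2: coverage of the ordinary interval.** Binomial data were simulated at the four per-arm sizes, with 1,000,000 trials per scenario. Trials were stopped by the Table 1 p-values using the pooled z, and log OR ± 1.96 × SE was computed at the stopping look, with SE = √(1/a + 1/b + 1/c + 1/d) over the four cells. Futility is non-binding, so both cases are shown:

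| True rates | Futility followed | Not followed |
|---|---|---|
| 30% / 30% | 94.9–95.0% | about 94.5% |
| 28% / 32% | 94.0% | 93.2% |
| 27.3% / 32.7% | 92.4–92.5% | 93.8–93.9% |
| 26.5% / 33.5% | 93.8% | 94.6% |

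Ranges are across repeat runs. Numerical integration gives 92.5% and 93.8% at the alternative. Over a grid of true odds ratios from 1.0 to 1.6 the lowest coverage was 92.3%, at 1.30, so the plan's alternative lies close to the worst case.

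**Step 3: conflict with the test.** If every stop follows Table 1, an efficacy stop at looks 1 to 3 has p ≤ 0.0147 and a futility stop has p ≥ 0.2424. The ordinary interval excludes 1 in the first case and includes it in the second, so it agrees with the decision. Conflict is left only at the final look, for p above 0.044 and up to 0.05. Its frequency is 0.4–0.5% under the null, 1.5–1.8% at 28% versus 32%, and 0.8–1.0% at the alternative. Over true odds ratios of 1.0 to 1.3 it is about 0.4–1.9%, highest near 1.15 to 1.2.

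Example: 387 versus 435 events of 1419 per arm.
- Test: pooled rate 822/2838 = 0.2896; difference 48/1419 = 0.03383; SE = √(0.2896 × 0.7104 × 2/1419) = 0.01703; z = 1.986; p = 0.047. This is above 0.044, so H0 is not rejected.
- Ordinary interval: OR = (435 × 1032)/(984 × 387) = 1.179; log OR = 0.1645; SE = √(1/387 + 1/435 + 1/1032 + 1/984) = 0.0829. Then 0.1645 ± 1.96 × 0.0829 gives 1.002 to 1.387, which excludes 1.
- With 2.014 in place of 1.96 the interval is 0.998 to 1.393, in line with the test.

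**Step 4: what a repeated interval does.** Using the Table 1 critical value at the stopping look, coverage is 99.1% (futility followed) and 97.7% (not followed) at the alternative, and 95.4% and 95.0% under the null. Relative width on the log scale is 2.014/1.96 = 1.03 at the final look, and 2.440/1.96 = 1.24, 2.820/1.96 = 1.44 and 3.156/1.96 = 1.61 after stops at looks 3, 2 and 1.

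**The case against.** The strongest reply is that the plan is silent rather than wrong. It names no interval method, so every coverage figure depends on an assumed ordinary interval. That is true, and the point is put conditionally. But an unqualified 95% interval, beside a 0.05 level stated for the primary analysis without the word overall, would by default be computed with 1.96.

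A second reply is that the shortfall is small: 92.4% is near the worst case and needs a non-binding futility rule to be followed every time. This also stands, and it limits the weight of the point.

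Third, the repeated interval is further from 95% at the alternative (97.7% to 99.1%) than the ordinary one, though on the safe side. This stands as a reason not to insist on that method over a stagewise-ordered interval.

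Some stronger readings are tempting but not supported:
- *The reader could not tell whether interval or test decides.* The plan makes the chi-square test primary and Table 1 states what rejects H0. The interval has no decision role, so the test governs.
- *The conflict can arise only at the final look.* That holds only if stops follow Table 1. The plan offers those rules to the Data Safety Monitoring Board for reference, and Data Management and Quality Assurance lets the Executive Committee with the IRB stop for adverse events. A stop at an interim with p between that look's threshold and 0.05 would produce the same conflict.
- *The trial's error rate is inflated.* Step 1 shows that it is not.

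**Conclusion.** The point holds as a modest gap that should be closed. The planned interval is not linked to the looks. Computed by default, it misses its stated level by about 1.1 to 2.6 points at the plan's alternative (95 − 93.9 and 95 − 92.4) and by at most about half a point under the null. In a small share of trials it would exclude 1 beside a test that does not reject. The test, boundaries and sample size are unaffected.

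The figures assume a Wald interval for the unadjusted odds ratio, looks at the Table 1 sizes, and efficacy stops that follow Table 1. The plan also says that strongly prognostic baseline variables "will be included in the covariate adjustment in the primary and secondary analyses". Whether the reported odds ratio is adjusted is a separate question, and the present point does not depend on it.

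**What to change.** Add one sentence after the interval statement in the Statistical Analysis Plan: the primary 95% interval for the odds ratio will be consistent with the group sequential design, by a method fixed before the first look. Either of two methods would serve:

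- **Repeated 95% interval:** log OR ± the efficacy critical value at the stopping look × SE. The values are 3.156, 2.820, 2.440 and 2.014 at the Table 1 sizes; otherwise they are recomputed from the gamma = −4 spending function at the actual information fractions. The recomputation clause is useful because the plan also dates its looks by calendar: "analyses will be performed at six months, one year, one and half year, and two year".
- **Stagewise-ordered 95% interval:** narrower, and equally acceptable if chosen in advance.

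The ordinary 95% interval may be shown as secondary, labelled as unadjusted for the looks.

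The cost is one sentence and a short calculation. The repeated interval is conservative and wider by the factors in Step 4. It would still differ from the test in about 0.3% of trials at the alternative, because the interval uses a Wald variance and the test a pooled one. Nothing else in the design changes.

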Appendix 1. Case Report Form

Table 1. Baseline Continuous Variables

Demographics
Age at surgery (years)
Height (cm)
Weight (kg)
Body mass index (kg/m ²)
Body surface area (m ²)
Preoperative Laboratory Values
Hematocrit (%)
Bilirubin (mg/dl)
Albumin (g/dl)
Blood urea nitrogen (mg/dl)
Serum creatinine (mg/dl)
Triglycerides (mg/dl)
High density lipoprotein cholesterol (mg/dl)
Low density lipoprotein cholesterol (mg/dl)
Red cell mass estimate (L)

Table 2. Baseline Categorical Variables

Preoperative Cardiac Variables
Myocardial infarction
Cardiogenic shock
Intra-Aortic balloon pump
Emergency surgery
Unstable angina
Atrial fibrillation
Left ventricular ejection fraction (EF)
EF>60%
EF=50-59%
EF=46-49%
EF=41-45%
EF=35-40%
EF<35%
New York Heart Association functional class
1
2
3
4
Reoperation number 0-3
0
1
2
3
Coronary artery disease (>70%)
Left circumflex disease
Left main disease
Left anterior descending disease
Right coronary artery disease
Preoperative Valve Pathology
Aortic valve regurgitation
Aortic valve stenosis
Mitral valve regurgitation
Comorbidities
Chronic obstructive pulmonary disease
Smoking
Hypertension

Diabetes: insulin dependent
Diabetes: non-insulin dependent
Stroke
Peripheral vascular disease
Renal disease
Alcohol use
Operative Factors
Aortic Cross clamp time (minutes)
Cardiopulmonary bypass time (minutes)
Internal thoracic artery grafting use
Procedure performed

Table 3. Outcome Variables as defined by Cleveland Clinic CTA and CVIR

Postoperative Complications
Hospital death
Neurological Morbidity
Encephalopathy
Focal deficit
Global deficit
Pulmonary Morbidity
ARDS
Aspiration pneumonia
Pneumonia
Pulmonary edema
Tracheostomy
Pulmonary embolus
Plural effusion
Hours on ventilator in intensive care unit
Renal Morbidity
Renal failure
Anuria
Renal protective dopamine
Infectious Morbidity
Sternal wound infection
Mediastinitis
Septicemia/ sepsis
Endocarditis
Cardiac Morbidity
Low cardiac output
Cardiac arrest
Atrial fibrillation
Myocardial infarction
Intra/Postop IABP
Anti-arrhythmics
Inotropic agents
Vasopressors
Multisystem organ failure
Reoperation for bleeding / tamponade

Table 4. Outcome Variables as defined by STS data collection

Mortality
Hospital death
Neurologic Morbidity
Transient stroke
Coma
Cerebral vascular accident
Pulmonary Morbidity
Pneumonia
Pulmonary embolus
Respiratory insufficiency
Prolonged ventilation
Renal Morbidity
Renal failure
Infectious Morbidity
Deep Sternal wound infection
Septicemia/ sepsis
Septicemia
Superficial wound infection
Urinary tract infection
Leg harvest site infection
Cardiac Morbidity
Atrial fibrillation
Myocardial infarction
Complete heart block
Ventricular tachycardia
Ventricular fibrillation
Asystole
Gastrointestinal Morbidity
Multisystem organ failure
Return to operating room for bleeding / tamponade
Reopen for graft occlusion, valve dysfunction, noncardiac reasons
Aortic or femoral artery dissection
Acute limb ischemia

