Cleveland Clinic Heart Center is a large tertiary care center and is among the busiest cardiac surgical centers in the US. Our annual volume over the last 5 years for coronary artery bypass grafting, and valve procedures has been between 3500-3790 surgeries. Transfusion of RBC currently occurs in approximately 40-50% of these patients.

Inclusion Criteria

All primary and reoperative adult cardiac surgical patients undergoing cardiopulmonary bypass for coronary artery bypass grafting, coronary artery bypass grafting with a valve procedure, isolated valve procedures and ascending aortic aneurysm or dissection repair alone or combined with CABG and valve procedures.

Exclusion criteria:

Age less than 18 years, descending thoracic aortic aneurysm repairs, left or right ventricular assist devices, and those unwilling to receive blood for religious reasons (Jehovah Witness).

Protocol

Our primary aim is to determine whether increased length of storage of RBC is related to adverse perioperative outcomes.

Study Intervention

Consecutive consenting patients who meet the inclusion criteria will be randomized to 'age of blood' less than two weeks or greater than 20 days shelf life for all of the units allocated to the patient. Red blood cell and component transfusion will follow management decisions of the care team. Adherence to the treatment protocol will be required for the patients in the operating room, intensive care unit and postoperatively until discharge from the hospital. Good clinical judgment supersedes the protocol.

Measurements

Baseline Information:

Baseline demographics, laboratory values, comorbidity, surgical procedure, operative variables, and postoperative morbid events are contained in Appendix 1. (CRF). These variables are routinely prospectively collected by the Departments of Cardiothoracic Anesthesia and Thoracic and Cardiovascular Surgery Cardiovascular Information Registries. These research registries have been approved by the institutional Internal Review Board for research purposes. Individual patient consent has been waived. Anesthesia automated record keeping system (ARKS) currently stores all hemodynamic information, intraoperative medication usage, arterial blood gas analyses, amount of crystalloid administered, time, number and identification number for RBC units transfused. Component blood product use and urine output are also automatically recorded and stored within the automated system.

Primary Outcome

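### The covariate rule does not exclude bypass time, cross-clamp time and other operative factors filed as baseline, so adjusted analyses could condition on post-randomisation variables

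*Combined protocol and SAP*

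**What the plan says.** Four places in the combined protocol and SAP bear on this.

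- **Timing of allocation** (Statistical Analysis Plan, randomization paragraph): "Before the start of surgery, the research coordinator responsible for randomization will check the randomization list".
- **Period of study treatment** (Study Intervention): "Adherence to the treatment protocol will be required for the patients in the operating room, intensive care unit and postoperatively until discharge from the hospital".
- **List of baseline variables** (Appendix 1): the table headed "Table 2. Baseline Categorical Variables" closes with a sub-block of operative factors. Its four entries are "Aortic Cross clamp time (minutes", "Cardiopulmonary bypass time (minutes", "Internal thoracic artery grafting use" and "Procedure performed".
- **Covariate rule** (Statistical Analysis Plan, first paragraph): after promising a descriptive comparison of the arms on the baseline variables, it says that "those that are believed to be strongly correlated with the outcomes will be included in the covariate adjustment in the primary and secondary analyses".

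No covariate is named, and no sentence limits the candidates to measurements made before allocation. Later in the same section the primary analysis is defined as a two-sided chi-square test with an odds ratio. The sample size section is built on that test.

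**The concern.** Covariate adjustment in a randomised trial is safe when the covariates are fixed before allocation. A variable that treatment may change is different. If it lies between treatment and outcome, adjusting for it removes part of the effect under study. If it also shares unmeasured causes with the outcome, adjusting for it can add further bias.

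The background sections argue that older cells impair oxygen delivery and microvascular flow. If that affected the course of the operation, bypass time and cross-clamp time could lie on the causal path. They are also natural candidates under a rule that selects on correlation with outcome. The adjusted odds ratio would then no longer estimate the effect of assignment. There is a smaller presentational cost: a baseline table containing these items would show post-allocation data as if they described the starting balance of the arms.

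**Working it through.** **1. Order of events.** Allocation is read before surgery. Assigned blood applies from the operating room to discharge. Cross-clamp and bypass times are complete only once those phases of the operation end, so study units can be given before either value is final. Graft use and procedure are recorded as done, which is also after allocation.

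**2. What the covariate rule admits.** The rule draws on baseline variables. The only itemised lists with that label are Appendix 1, Tables 1 and 2, and Table 2 contains the operative block. The filter is believed correlation with outcome, not time of measurement. These items can therefore pass, but nothing says that they will. The Preliminary Studies section makes it plausible that they would: the long-term survival model adjusted for operative factors, and the functional-recovery model adjusted for operative factors, surgical procedure and postoperative events.

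**3. The plan's own sample size.** Inputs from the sample size section: 27.3% and 32.7%, two-sided 0.05, power 0.85.

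- Without continuity correction: n = [1.960 × √(2 × 0.30 × 0.70) + 1.036 × √(0.273 × 0.727 + 0.327 × 0.673)]² / 0.054² = 1291.6, so 1292 per arm.
- With continuity correction: n = (1291.6 / 4) × [1 + √(1 + 4 / (1291.6 × 0.054))]² = 1328.4 per arm.

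The plan states 1328 per arm, 2656 in total, so its figure reproduces. No covariate enters the formula. Restricting the adjustment therefore leaves 2656 and the sequential maximum of 2838 unchanged.

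**4. Possible size of the bias.** None of the following inputs comes from the documents except the planned odds ratio of 1.3. Assume that older blood shifts bypass time by s SD, that the log odds of the composite rise by g per SD of bypass time, and that bypass time is normal within arm. Hold the marginal odds ratio at 1.30 (ln 1.30 = 0.262), with 27.3% in the newer-blood arm. The odds ratio is non-collapsible, so first find by numerical integration the conditional log odds ratio b₀ that gives a marginal 1.30 when s = 0. In this model the adjusted log odds ratio is then exactly b₀ − s × g.

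| Odds ratio per SD | g | Adjusted OR, s = 0 | s = 0.05 | s = 0.1 |
|---|---|---|---|---|
| 1.4 | 0.336 | 1.308 | 1.286 | 1.265 |
| 2.0 | 0.693 | 1.333 | 1.287 | 1.244 |

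First row, s = 0.1: ln 1.308 − 0.1 × 0.336 = 0.2685 − 0.0336 = 0.2349, and exp(0.2349) = 1.265. Second row, s = 0.1: 0.2873 − 0.0693 = 0.2180, and exp(0.2180) = 1.244. Against 0.262 these log odds ratios are 10% and 17% lower. At s = 0.05 they are about 4% lower. The s = 0 column exceeds 1.30 only because a conditional odds ratio differs from a marginal one; that is not bias.

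**5. Sensitivity to a shared unmeasured cause.** This was simulated with 400,000 patients, a log odds ratio of 0.4 per SD for bypass time, and a common cause with correlation 0.5 with bypass time and its own log odds ratio of 0.4. At s = 0.1 the unadjusted odds ratio was 1.27 and the adjusted 1.21. At s = 0 they were 1.28 and 1.30. Simulation error is about 0.01. These inputs are also assumed.

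**The case against.** The strongest reply is that this is loose labelling on a form and not an analysis decision. Two continuous times sit in a table titled categorical, under their own operative sub-heading, apart from the preoperative items. The Baseline Information paragraph also mentions operative variables, but the same sentence lists postoperative events, so that heading describes where data are held and does not define baseline. The covariate rule does not cite Appendix 1. All of this stands. It means that a reader who infers that the plan will adjust for bypass time goes further than the text, which only leaves the possibility open.

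A reader might also infer that the main result is compromised. The documents do not support that, because the chi-square test takes no covariates. The first paragraph of the Statistical Analysis Plan does speak of adjustment in the primary analysis. That disagreement needs reconciling, but it is a separate matter; the primary result is exposed here only if the adjustment is carried out.

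The four items are also unequal. Eligibility is defined by type of operation, so procedure is largely known beforehand, and graft use may largely follow the preoperative plan. For a patient first transfused after surgery, study blood cannot have altered any of them. The documents do not give the share transfused in the operating room, and any bias is diluted accordingly.

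Finally, one might subtract s × g directly from ln 1.30 and report adjusted odds ratios of 1.26 to 1.21 at 0.1 SD, a loss of 13% to 26%. That takes a conditional quantity from a marginal one and overstates the drop from the planned 1.30.

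What the reply does not remove is that the only itemised baseline lists include post-allocation variables, and that the selection rule has no timing condition.

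**Conclusion.** The point holds as a gap in the covariate rule. As written, the adjusted analyses of ventilation, atrial fibrillation and lengths of stay, and of the composite if it is adjusted, could condition on post-randomisation variables. Bypass and cross-clamp time are the ones that matter most. The unadjusted primary test, its odds ratio and the sample size are untouched.

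The size cannot be derived from the documents, because they give no effect of storage age on operative times. For the composite, under the stated assumptions, a true marginal odds ratio of 1.30 would appear after adjustment as about 1.24 to 1.27 at a 0.1 SD shift and about 1.29 at 0.05 SD. With no shift there is no bias by this path. A shared unmeasured cause would lower the adjusted figure further if there is a shift. These are illustrations, not predictions. I would label this a cheap improvement.

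**What to change.** - In the Statistical Analysis Plan, state that only variables known before allocation may enter any covariate adjustment, primary or secondary. Preferably name them in advance.
- Use the procedure planned at allocation in place of the procedure performed.
- Exclude bypass time, cross-clamp time and internal thoracic artery use from the candidate covariates.
- Take the operative block out of the baseline part of Appendix 1 and report it descriptively by arm, as intraoperative, post-randomisation data.

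The cost is SAP and case report form wording, including an entry for planned procedure if it is not already captured. Sample size and stopping boundaries do not change. The one statistical downside is some loss of prognostic precision in the adjusted analyses, even if storage age has no effect on operative times. Age, ejection fraction, reoperation number, preoperative laboratory values and planned procedure remain available, so the loss should be small.
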